| RMT | Remote Measurement Technologies |
| (S)AE | (Serious) Adverse Event |
| SFS | Social Functioning Scale |
| Sponsor | The sponsor is the party that commissions the organisation or performance of the research, for example a pharmaceutical company, academic hospital, scientific organisation or investigator. A party that provides funding for a study but does not commission it is not regarded as the sponsor, but referred to as a subsidising party. |
| SUSAR | Suspected Unexpected Serious Adverse Reaction |
| VSWM | Visuo-Spatial Working Memory |
| WMO | Medical Research Involving Human Subjects Act |

Evaluation of a Computerized Complex Instrumental Activities of Daily Living Marker (NMI) (AltoidaML)

SUMMARY

Alzheimer's disease (AD) is associated with staggering costs and suffering, which are particularly related to the social impacts of caring for increasingly disabled individuals. These functional disabilities can be almost undetectable in the early stages of the disease, worsening over time often and at a varying rate of progression in different people. The measurement of such functional disabilities is typically blunt and relies on direct observation or caregiver recall. Digital technologies, particularly those based on the use of smartphones, wearables and/or home-based monitoring devices, here defined as 'Remote Measurement Technologies' (RMTs), provide an opportunity to change radically the way in which functional assessment is undertaken in AD. RMTs have the potential to obtain better measurements of behavioural and biological parameters associated with individual Activities of Daily Living (ADL) when compared to the current subjective scales or questionnaires. Divergence from normative ADL profiles could objectively indicate the presence of specific incipient functional impairments even at the very early stages of AD. Therefore, the main hypothesis of this project is that RMTs should allow the detection of impairments in functional component of ADLs that occur below the threshold of clinical scale detection or disability questionnaires.

Objectives: The primary objective of this study is to assess the performance of selected RMTs against standardised rating scales of ADLs in subjects with preclinical AD dementia, MCI due to AD dementia, and mild-to-moderate AD dementia. Secondary objectives are, (a) to evaluate associations between RMTs and standard clinical scales used to characterise people with AD diagnosis, (b) to investigate the patient acceptability of selected RMTs used for the duration of the study, and (c) to assess the technical performance of RMTs and digital platform in a real-life setting.

Study design: A multicentre observational cross-sectional cohort digital assessment study lasting 5 years, with a sub-study extension of at-home monitoring for 4 weeks.

Study population: Subjects (n=283) with positive AD biomarkers, e.g positive brain Abeta (A β) deposition confirmed by amyloid PET or CSF A β test at the preclinical AD, MCI due to AD, and mild-to-moderate AD dementia stages, and age-and gender matched control subjects (n=213) aged over 50 years with a caregiver/family member available to contribute to the study.

Primary outcome measure: statistically significant difference between healthy volunteers, preclinical AD, MCI due to AD, and mild-to-moderate AD dementia in outcome measures of ADL using selected RMTs.

1. **Secondary Outcome measurements:** Statistically significant difference between healthy volunteers, preclinical AD, MCI due to AD, and mild-to-moderate AD dementia using RMTs, neuropsychological assessment like CDR and Altoida's cognitive scale. Finally the relationship of genes or biomarkers with risk of RMT progression, and longitudinal correlation changes in biomarkers with rate of RMT progression.

Evaluation of a Computerized Complex Instrumental Activities of Daily Living Marker (NMI) (AltoidaML)

2. Assess effectiveness of disease modifying therapy such as aducanumab in real world clinical practice on subjects who will initiate disease modifying therapy for AD treatment during the study by using neuropsychological assessment such as CDR and fluid biomarker including blood and CSF and so on.
3. Assess effectiveness of disease modifying therapy such as aducanumab in real world clinical practice on subjects who will initiate disease modifying therapy for AD treatment during the study by using RMTs and Altoida's cognitive scale.

Nature and extent of the burden and risks associated with participation, benefit and group relatedness: Subjects will visit the clinic at least thirteen times: once for a baseline visit and once at the end of the study. During these visits, information gathering, clinical profiling, neurophysiological testing and training in the use of RMTs will be performed. Up to fourteen telephone interviews will be held during the study duration of 5 years to assess user experience, technical problems with the RMTs and adverse events. The study will not have any direct benefits for participants.

Evaluation of a Computerized Complex Instrumental Activities of Daily Living Marker (NMI) (AltoidaML)

1. INTRODUCTION AND RATIONALE

Alzheimer's disease (AD) is a progressive neurodegenerative disorder characterized by a cascade of pathological events, including abnormal extracellular deposition of amyloid-beta (A β) plaques, intracellular tau tangles, and volumetric loss of cortical gray matter (Jack et al. 2018). Clinically, AD is characterized by several syndromic stages defined by a combination positive biomarker signals (e.g., A β load in CSF or brain tissue), various levels of cognitive impairment and different stages of dementia. Current consensus is that AD pathophysiology is already present in the brain long before the onset of clinical symptoms. This so-called 'preclinical' disease phase can last for up to 20 years, being characterised primarily by biomarker positivity despite normal cognitive performance. The first clinical symptom generally observed in AD patients is short-term memory deficits, sometimes associated with modest impairments in other cognitive domains. This syndromic phase is referred to as 'prodromal AD' or Mild Cognitive Impairment (MCI) stage. As the disease progresses, AD patients experience a progressive loss of cognitive capacities in multiple domains, which significantly interfere with activities of daily living (ADL). This final syndromic phase is referred to as the 'dementia' stage of AD typically subdivided in mild, moderate AD and severe AD dementia, based on the severity of cognitive impairment and the levels of functional decline.

Especially when patients reach the dementia stage of AD, the disorder is associated with staggering costs to the health care system, health insurance and families. These costs relate particularly to the social-and economic impacts of caring for individuals with increasing functional disabilities. These functional disabilities start as almost undetectable in the preclinical disease phase, worsening over time, often at varying rates in different people at the MCI due to AD stages. A very early detection of the presence of functional decline in preclinical AD may eventually help in adopting a different lifestyle or motivate the acceptance of effective therapeutic intervention, at least those presently available. However, current standard measurements of functional disabilities based on scales or questionnaires are typically blunt and insensitive to change. The main reason is that the scores are based on either individual self-appreciation, caregiver recall or physician-rated direct observations (subjective). Scoring these scales or filling questionnaires based on predefined syndromic constructs that require judgement about the "average" performance occurring in periods spanning through either weeks or months (integration over large time-span), hence only very modestly accurate. In addition, measurement of disabilities is typically performed once every several months (low frequency) and during hospital visits (clinical setting). RMT digital technologies such as smartphones, wearable devices, e.g. actigraphy and home-based monitoring devices can provide an opportunity to change radically the way in which functional assessment is undertaken in AD. The build in sensors are non-invasive, ie patients are not

Evaluation of a Computerized Complex Instrumental Activities of Daily Living Marker (NMI) (AltoidaML)

aware of measurements being taken and allow detailed measurements of parameters associated to symptoms or specific behaviour (objective) and of activities of direct relevance for quality of life (ecological), measured when the behaviour occurs (momentarily, high frequency), either measured continuously or once/twice day over months (high frequency), generally performed at home or outdoor (non-clinical setting, real life) without the need to frequently visit a hospital. Ultimately, such technologies may allow us to move from a “diagnose and treat” to a “predict and preempt” model of care [1]. This approach will become of value when reliable therapeutics aimed to slow down the progression of the disease will be available hopefully allowing patients in the earliest stages of AD to live independently for longer. Unfortunately, despite considerable progress in our understanding of the neuropathology of AD, this progress has not been translated into novel drug treatments, partially due to the low assay sensitivity of the clinical measurements included so far in the clinical studies. Therefore, RMT may provide a possible solution to this problem.

The current study is part of the Innovative Medicine Initiative (IMI) funded Remote Assessment of Disease And Relapse (RADAR) consortium. The goal of RADAR-AD is the development and initial validation of technology-enabled, quantitative and sensitive measures of functional decline by assessing Activities of Daily Living (ADL) in patients in various stages of the AD progression. The RADAR-AD team has identified and singled out from the literature a series of functional disabilities that potentially affect the subject's daily life in early phases of the AD. Relevant outcome measures for the study have been selected through the following longitudinal process:

1. Identification of functional domains that meet one or more of the following criteria:
 - Predicts conversion of MCI due to AD to mild AD dementia.
 - Impaired in mild AD dementia.
 - Predicts functional decline in AD dementia.
 - Reported as important by an AD dementia patient advisory board.
2. Identification of candidate RMT to cover real-life measurement of the functional domains identified in step 1.
3. Identification of candidate digital biomarkers to cover clinical measurement of the functional domains identified in step 1.

Functional domains, RMTs, and clinical assessments that resulted from the selection process above are listed in Tables 1, and 2. The selection process described in step 1 resulted in the identification of the following functional domains, sorted by relevance (HR=highly relevant, R=relevant, N=neutral, LR=least relevant). See appendix A for a reference list regarding the functional domain selection process.

Table 1: selected functional domains and their relevance

Evaluation of a Computerized Complex Instrumental Activities of Daily Living Marker (NMI) (AltoidaML)

| Functional domain | Relevance | Predicts MCI->AD dementia conversion | Impaired in early AD | Predictive of decline | Reported by PAB |
|--|-----------|--------------------------------------|----------------------|-----------------------|-----------------|
| 1. Difficulties at work | HR | x | X | x | x |
| 2. Spatial navigation & memory | HR | x | X | x | x |
| 3. Planning skills & memory required for task-completion | HR | x | X | x | x |
| 4. Managing finances | R | x | | x | x |
| 5. Self-care | R | | X | x | x |
| 6. Self-management, e.g., running errands & shopping | R | x | | x | x |
| 7. Acquiring new skills | R | | X | x | x |
| 8. Sleep quality & circadian rhythms | R | | X | x | x |
| 9. Use of technology/devices | R | | X | x | x |
| 10. Dysnomia, word finding difficulties | N | | X | x | |
| 11. Gait | N | | X | x | |
| 12. Difficulties driving | N | | X | x | |
| 13. Interpersonal interaction | N | | X | | x |
| 14. Motivation, signs of apathy or withdrawal | LR | | | | x |

The central assumption of the study is that functional disabilities proportionally increase with the progressive worsening of the disorder. A recent classification proposed by the FDA 2018 guidelines for the development of novel treatments in Preclinical AD identifies the early disease progression in 3 stages: (a) Patients with characteristic pathophysiologic changes of Preclinical AD but no evidence of clinical impact (Stage 1) (b) Patients with characteristic pathophysiologic changes of AD and subtle or more apparent detectable abnormalities on sensitive neuropsychological measures, but no functional impairment (Stage 2), and (c) Patients with characteristic pathophysiologic changes of AD and subtle or more apparent detectable abnormalities on sensitive neuropsychological measures, but mild and detectable functional impairment. (Stage 3). The aim of the RADAR-AD study is to assess the feasibility, utility and performance of selected RMTs in profiling ADL in real-world settings [2, 3]. This goal will be achieved by evaluating digital signals collected either continuously, or daily, or weekly at home, either using wearable devices or home-located ambient devices, determining as much as possible the specific context-dependent conditions in which the signals are measured. As a general hypothesis, we expect that RMTs will deliver more sensitive and less variable measurements when compared to standard clinical assessments, questionnaires and tests measuring specific functional capabilities in the clinics.

The most important results of the present study will be (1) the evidence that some RMT parameters will provide insights for lower variance than the standard scales or

Evaluation of a Computerized Complex Instrumental Activities of Daily Living Marker (NMI) (AltoidaML)

questionnaires, (2) the capacity of Altoida's NMI¹ and/or RMT to significantly differentiate the preclinical AD stages 1 & 2 when compared to healthy control, and (3) similar capabilities of Altoida's NMI and/or RMT to detect monotonic change in the MCI due to AD group and, even more, in mild-to-moderate AD dementia groups, proportional to the specific functional impairment known to worsen during the disease progression. A similar outcome to point 3 above, was obtained using the computerised Amsterdam-iADL scales [4, 5], showing a significant change in the group of individuals with subjective cognitive decline over time, resembling cognitive trajectories of the preclinical AD group of the RADAR-AD study.

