2. OBJECTIVES & OUTCOMES

1. Objectives

The main objective is to assess the performance of selected RMTs against ADL standard clinical questionnaires in finding differences among individuals of various classes of severity of AD and investigate if RMT measurements are more precise and better reflect disease progression and functional /QoL changes compared to ADL standard measurements.

Secondary objectives:

- to assess associations between RMT measurements and standard clinical scales used to assess specific clinical conditions and functional impairments in AD patients;
- to assess if RMT measurements are more precise and more ecological;
- to investigate the patient acceptability and user-friendliness of selected RMTs;
- to assess the technical performance of RMTs in a real-life setting.
- to assess associations between RMT measurements, standard clinical scales and AD-related biomarker in blood and CSF
- to explore new AD-related biomarkers.

To achieve the non-invasive aspect of these objectives, measurements will be performed in clinic (i.e. under supervision of a clinical team) and in non-clinical, real life settings (i.e. at home, at work, etc.).

Primary Outcome

- Difference between healthy controls, subjects with preclinical AD, subjects with MCI due to AD, and subjects with mild-to-moderate AD dementia using selected RMTs measurements aimed to profile ADL, using diagnostic criteria as defined under 3.1.3" Both primary and secondary outcomes.

¹ Buegler, M, Harms, RL, Balasa, M, et al. Digital biomarker-based individualized prognosis for people at risk of dementia. *Alzheimer's Dement*. 2020; 12:e12073. <https://doi.org/10.1002/dad2.12073>

Evaluation of a Computerized Complex Instrumental Activities of Daily Living Marker (NMI) (AltoidaML)

Secondary Outcomes

- Established clinical measures: difference between healthy volunteers, subjects with preclinical AD, subjects with MCI due to AD, and subjects with mild-to-moderate AD dementia in the following assessments of specific functions when performed in the clinic (in brackets, it is indicated which functional domain and/or main outcome measure is covered by the assessment):
 - Amsterdam-iADL
 - (orientation, planning skills & memory required for task completion household management).
 - ADCS-ADL
 - (orientation, planning skills & memory required for task completion household management).
 - CERAD neuropsychological test battery

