6. STATISTICAL ANALYSIS

Data obtained from RMTs will be either continuous (as, for example, accelerometer recording having several samples per second, participant's relative locations recorded via GPS every 5 minutes, ...) or obtained during a single clinical visit only (as, for example, gait assessment). Continuous raw data will be analytically processed and features characterizing behaviour per day will be obtained. For example, actigraphy read-outs will be used to derive sleep characteristics using Cole-Kripke algorithm (duration, quality of sleep, etc.) for every night, relative location data will be used to estimate distance travelled per day, duration of home stay per day, number of places visit per day and so on. Complete strategy for handling multi-sensor data and list of relevant features will be developed through the project duration. At the end, RMT data will be either a day-by-day time series or obtained at a single study time point.

We will analyse each RMT measurement separately, characterizing their variance to assess, whether 1) they are different between following groups: (a) healthy volunteers and (b) subjects with preclinical AD, (c) subjects with MCI due to AD, and (d) subjects with mild-to-moderate AD dementia, and 2) whether they are related to standard clinical questionnaires for ADL. For a continuous day-by-day time series, we will model such a RMT measure using a mixed-effect model for repeated measures (MMRM) based on observed case data. The model will include study group (or a related ADL scale), age, sex, and other related covariates/factors. Strength of between study groups difference (or relation to related ADL scale) is of primary interest. The within-participant covariance between visits will be estimated via an unstructured variance-covariance matrix. In case of convergence problems, alternative variance-covariance structures will be tried in the following order, with the first structure that converges being used in the analysis: heterogeneous Toeplitz, standard Toeplitz, and AR(1) with separate participant random effect. Weekdays and weekends time

Evaluation of a Computerized Complex Instrumental Activities of Daily Living Marker (NMI) (AltoidaML)

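### Lower variance than the standard scales is named as a leading result, but it cannot show that RMTs are more precise or sensitive, and no planned analysis fills the gap

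*Combined protocol and SAP*

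**What the plan says.** Section 1 (Introduction and Rationale) states the general hypothesis: "we expect that RMTs will deliver more sensitive and less variable measurements when compared to standard clinical assessments", questionnaires and clinic tests. It then lists three most important results. The first is evidence that "some RMT parameters will provide insights for lower variance than the standard scales or" questionnaires. The second is the capacity of the Altoida index and/or RMTs "to significantly differentiate the preclinical AD stages 1 & 2 when compared to healthy control". The third is detection of monotonic change through the MCI and dementia groups.

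Section 2 (Objectives & Outcomes) takes the idea into the main objective, which is in part to "investigate if RMT measurements are more precise and better reflect disease progression" and function than standard ADL measurements. A secondary objective repeats the wish to show greater precision.

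Section 6 (Statistical Analysis) fits a separate model to each RMT, with study group or a related ADL scale as the explanatory term. The "list of relevant features will be developed through the project duration", and multiplicity adjustment is mentioned only as something to consider.

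**The concern.** The documents do not say which variance is meant (between-person, within-person or residual). They set no common scale, name neither the RMTs nor the comparator scale for this result, and give no test or threshold. Three weaknesses follow.

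- RMT features include daily distance, time at home and number of places visited. The comparators are questionnaire scores. Which variance is lower depends on the unit chosen.
- Low variance is not precision. A measure that barely moves with disease stage can have a small variance and still be of no use for staging.
- The result asks only for some RMTs, from a list that is still open, so the favourable ones can be picked once the data are in.

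At stake is a headline claim. Result 1 could be reported for an RMT that separates the stages worse than the questionnaire does, and be read as meeting the precision part of the main objective.

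**Working it through.** **The plan's own figure.** None is given for the lower-variance result. The only powered figure is 55 per group (Section 3, Sample size calculation), for three Holm-adjusted Welch t-tests on the Amsterdam IADL, all of which must succeed. The interquartile ranges behind it are not printed, so it cannot be reproduced. It can be inverted: with three equal gaps and equal SDs, simulation gives 79% power at 55 per group for a gap of 0.66 SD and 82% for 0.68 SD. A gap of 10 units at 0.66 SD implies an SD of 10/0.66 = 15.2. I use this only to anchor the illustrations.

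**Units.** Multiplying a measure by c multiplies its variance by c² and leaves d = difference/SD unchanged. Expressing a timed test in minutes instead of seconds divides the variance by 60² = 3,600 with no change in information.

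**Variance against discrimination.** The values below are assumed. Power is for one two-sided 5% two-sample comparison at 55 per group.

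| Measure | Difference | SD | Variance | d | Power |
|---|---|---|---|---|---|
| Reference scale | 10 | 15.2 | 231 | 0.66 | 93% |
| Same scale divided by 10 | 1 | 1.52 | 2.3 | 0.66 | 93% |
| Insensitive RMT | 1 | 7.6 | 58 | 0.13 | 10% |
| Sensitive RMT | 25 | 30 | 900 | 0.83 | 99% |

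By lower variance, the insensitive RMT beats the scale with a quarter of its variance (58/231 = 0.25). The sensitive RMT loses with 3.9 times the variance (900/231). The ranking by d is the reverse.

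**Chance success with some of K RMTs.** K is not in the documents; I take 10 and 20. Suppose K RMTs and one scale have equal true variance on a common scale and are exchangeable. The scale then has the smallest of K+1 sample variances with probability 1/(K+1), so at least one RMT is lower with probability K/(K+1).

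| Rule for success | K = 10 | K = 20 |
|---|---|---|
| Any numerically lower sample variance, K/(K+1) | 10/11 = 91% | 20/21 = 95% |
| Uncorrected one-sided 5% F-test against the shared scale, n = 55 (simulated) | 27% | 38% |
| Any lower, RMTs correlated 0.8 with each other and independent of the scale (simulated) | about 75% | about 80% |

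The F-test figures change little with n: 25-26% for K = 10 and 35-36% for K = 20 at n = 220 and n = 498.

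**Is the objective answered elsewhere?** Section 6 contains per-RMT models (MMRM or ANCOVA) for group or ADL scale, multivariate prediction from RMT features, a Bland-Altman comparison of clinic and home versions of the same test, and a comparison of predictive performance between home and clinic assessments. The ADL-scale models measure association. None asks whether an RMT separates the stages better than the scale does in the same participants.

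**The case against.** The wording of result 1 is loose and sits in the rationale. The Introduction criticises the scales as subjective, infrequent and averaged over long periods, so the authors may well have measurement error within a person in mind. No raw-unit comparison is proposed anywhere. Sensitivity is also stated next to variability in the hypothesis, and next to precision in the main objective, while results 2 and 3 ask for separation and monotonic change. All of this is fair.

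It does not remove the point. A within-person or residual variance in raw units is still unit-dependent and still says nothing about signal. Results 2 and 3 are separate items, and nothing requires the same RMT to meet all three.

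A reader might infer that the plan contains a formal variance contest, because Section 6 says "We will analyse each RMT measurement separately, characterizing their variance to assess". The sentence goes on to group differences and to relations with questionnaires, so it concerns how each RMT's variation is explained. It is not a ranking against the scales. No variance test or success rule is planned.

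A reader might also take 91-95% as the false-success rate of the study. The documents do not support that. The figure needs an assumed K, exchangeable measures and a rule that any smaller sample variance counts.

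**Conclusion.** The point holds as a gap between a stated claim and the means of supporting it. Lower variance than the scales cannot establish greater precision or sensitivity, and the analysis section offers no other RMT-versus-scale comparison. The unit argument is exact. The power illustrations rest on assumed differences and SDs. The chance of false success is real but cannot be fixed from the documents: roughly 27-38% for 10 to 20 RMTs under uncorrected F-tests, higher if no test is applied, and lower if the RMTs are correlated with each other or a correction is made.

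It would go too far to conclude that the primary outcome or the sample size is compromised. The primary outcome is the difference between stage groups, the strength of that difference is what Section 6 puts first, and the 55 per group does not depend on result 1. This is a cheap improvement that protects interpretation.

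**What to change.** 1. In result 1 of Section 1, replace lower variance by a unit-free measure, and use the same measure in Section 2 to define what more precise means. A suitable choice is the covariate-adjusted difference between neighbouring stages divided by the residual SD; AUC would also serve.
2. Compute it for each RMT and for the Amsterdam IADL in the same participants, with a paired bootstrap interval for the contrast.
3. Commit to multiplicity control over all RMTs examined, and list those RMTs before the comparison is run.
4. For RMTs measured repeatedly, report the intraclass correlation as the measure of within-person reliability.
5. State that raw variances will not be compared across instruments.

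The cost is some rewording in Sections 1 and 2 and one paragraph in Section 6, using measures already planned. The downside is that a claim of superiority over the scales becomes harder to meet.
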